3. PRIMARY AND SECONDARY VARIABLES

3.1 Efficacy

3.1.1 Derivation of RECIST visit responses

For all patients, the RECIST tumour response data will be used to determine each patient’s visit response according to RECIST version 1.1. It will also be used to determine if, and when, a patient has progressed in accordance with RECIST and their best objective response to study drug.

Baseline radiological tumour assessments are to be performed no more than 28 days before the first dose of treatment, and as close as possible to the start of study treatment. Assessments on the day of the first dose where neither time nor a nominal pre-dose indicator are captured will be considered prior to the first dose if such procedures are required by the protocol to be conducted before the first dose. Tumour assessments are then performed every 8 weeks (± 1 week) following the start of study treatment until objective disease progression.

If an unscheduled assessment is performed, and the patient has not progressed, every attempt should be made to perform the subsequent assessments at their scheduled visits. This schedule is to be followed to minimise any unintentional bias caused by some patients being assessed at a different frequency than other patients.

From the Investigator's review of the imaging scans, the RECIST tumour response data will be used to determine each patient's visit response according to RECIST 1.1. At each visit, patients will be programmatically assigned a RECIST 1.1 visit response of complete response (CR), partial response (PR), stable disease (SD) or progressive disease (PD), using the information from target lesions (TLs), non-target lesions (NTLs) and new lesions and depending on the status of their disease compared with baseline and previous assessments. If a patient has had a tumour assessment that cannot be evaluated then the patient will be assigned a visit response of not evaluable (NE), (unless there is evidence of progression in which case the response will be assigned as PD).

Please refer to [Table 4](#) for the definitions of CR, PR, SD, and PD.

RECIST outcomes (ie, PFS, ORR etc.) will be calculated programmatically for the site Investigator data (see [Section 3.2](#)) from the overall visit responses.

Only patients with measurable disease at baseline should be included in the study. Measurable disease is defined by the presence of at least one measurable lesion which has not been irradiated and not chosen for biopsy during the screening period.

3.1.1.1 Target lesions

Measurable disease is defined as having at least one measurable (by RECIST 1.1) lesion, that has not been previously irradiated, which is ≥ 10 mm in the longest diameter (LD), (except lymph nodes which must have short axis ≥ 15 mm) with computed tomography (CT) or magnetic resonance imaging (MRI) and which is suitable for accurate repeated measurements. If only one measurable lesion exists, it is acceptable to be used (as a target lesion) as long as it has not been previously resected or irradiated and baseline tumour assessment scans are done at least 14 days after the screening biopsy is performed.

A patient can have a maximum of 5 measurable lesions recorded at baseline with a maximum of two lesions per organ (representative of all lesions involved and suitable for accurate repeated measurement) and these are referred to as target lesions (TLs). If more than one baseline scan is

recorded, then measurements from the one that is closest and prior to first dose of treatment will be used to define the baseline sum of TLs. Target lesions should be selected based on their size (longest diameter for non-nodal lesions or short axis for nodal lesions), but in addition should be those that lend themselves to reproducible repeated measurements. It may be the case that, on occasion, the largest lesion does not lend itself to reproducible measurement in which circumstance the next largest lesion, which can be measured reproducibly, should be selected.

All other lesions (or sites of disease) not recorded as TL should be identified as non-target lesions (NTLs) at baseline. Measurements are not required for these lesions, but their status should be followed at subsequent visits.

[Table 4](#) provides the definitions of the criteria used to determine objective tumour visit response for TL.

Table 4 **TL visit responses**

Visit Responses	Description
CR	Disappearance of all TLs since baseline. Any pathological lymph nodes selected as TLs must have a reduction in short axis to <10 mm.
PR	At least a 30% decrease in the sum of the diameters of TLs, taking as reference the baseline sum of diameters as long as criteria for PD are not met.
SD	Neither sufficient shrinkage to qualify for PR nor sufficient increase to qualify for PD.
PD	At least a 20% increase in the sum of the diameters of TLs, taking as reference the smallest sum on study (this includes the baseline sum if that is the smallest on the study). In addition to the relative increase of at least 20%, the sum must also demonstrate an absolute increase of at least 5 mm.
NE	Only relevant if any of the TLs were not assessed or not evaluable or had a lesion intervention at this visit. Note: If the sum of diameters meets the progressive disease criteria, progressive disease overrides not evaluable as a TL response.
NA	No TLs are recorded at baseline.

Abbreviations: CR = Complete response; NA = Not applicable; NE = Not evaluable; PD = Progressive disease; PR = Partial response; SD = Stable disease; TL = Target lesion.

Rounding of TL data

For calculation of PD and PR for TLs, percentage changes from baseline and previous minimum should be rounded to one decimal place before assigning a TL response. For example, 19.95% should be rounded to 20.0% but 19.94% should be rounded to 19.9%.

Missing TL data

For a visit to be evaluable, all TL measurements should be recorded. However, a visit response of PD should still be assigned if any of the following occurred:

- A new lesion is recorded.
- A NTL visit response of PD is recorded.
- The sum of TLs is sufficiently increased to result in a 20% increase, and an absolute increase of ≥ 5 mm, from nadir (defined below) even assuming the non-recorded TLs have disappeared.

The nadir (ie, the smallest measurement based on the same set of lesions at baseline and on a given visit) can only be taken from assessments where all the TLs had a longest diameter (LD) recorded.

Lymph nodes

For lymph nodes, if the size reduces to <10 mm, these are considered non-pathological.

However, a size will still be measured, and this size should still be used to determine the TL visit response as normal. In the special case where all lymph nodes are <10 mm and all other TLs are 0 mm, then although the sum may be >0 mm, the calculation of TL response should be overwritten as a CR.

TL visit responses subsequent to CR

A CR response can only be followed by CR, PD or NE. If a CR has occurred, then the following rules at the subsequent visits must be applied:

- Step 1: If all lesions meet the CR criteria (ie, 0 mm or <10 mm for lymph nodes), the response will be set to CR irrespective of whether the criteria for PD of TL is also met for lymph node (ie, if a lymph node LD increases by 20% but remains <10 mm).
- Step 2: If some lesion measurements are missing but all other lesions meet the CR criteria (ie, 0 mm or <10 mm for lymph nodes), the response will be set to NE irrespective of whether the criteria for PD is also met when referencing the sum of TL diameters.
- Step 3: If not all lesions meet the CR criteria, and the sum of lesions meets the criteria for PD, the response will be set to PD.
- Step 4: If, after steps 1 through 3, a response can still not be determined, the response will be set to remain as CR.

TL too big to measure

If a TL becomes too big to measure, this should be indicated in the database and an estimated size ('x') above which it cannot be accurately measured should be recorded. If using a value of x in the calculation of TL response would not give an overall visit response of PD, then this will be flagged and reviewed by the study team. It is expected that a visit response of PD will remain in the vast majority of cases.

TL too small to measure

If a TL becomes too small to measure, then this will be indicated as such on the case report form and a value of 5mm will be entered into the database and used in TL calculations. However, a smaller value may be used if the radiologist has not indicated 'too small to measure' on the case report form and has entered a smaller value that can be reliably measured. If a lesion has completely disappeared, the longest diameter should be recorded as 0 mm.

Irradiated lesions/lesion intervention

Previously irradiated lesions (ie, lesion irradiated prior to entry into the study) should be recorded as NTLs and should not form part of the TL assessment.

Any TL (including lymph nodes) which has had intervention during the study (for example, irradiation/palliative surgery/embolization) should be handled in the following way and once a lesion has had intervention then it should be treated as having intervention for the remainder of the study, noting that an intervention will most likely shrink the size of tumours:

- Step 1: The diameters of the TLs (including the lesions that have had intervention) will be summed and the calculation will be performed in the usual manner. If the visit response is PD this will remain as a valid response category.
- Step 2: If there was no evidence of progression after step 1, treat the lesion diameter (for those lesions with intervention) as missing and, if $\leq 1/3$ of the TLs have missing measurements, scale up as described in the scaling section below. If the scaling results in a visit response of PD then the patient would be assigned a TL response of PD.
- Step 3: If after both steps PD has not been assigned, then, if appropriate (ie, if $\leq 1/3$ of the TLs have missing measurements), the scaled sum of diameters as calculated in step 2 should be used, and PR or SD then assigned as the visit response. Patients with intervention are evaluable for CR as long as all non-intervened lesions are 0 (or < 10 mm for lymph nodes) and the lesions that have been subject to intervention also has a value of 0 recorded. If scaling up is not appropriate due to too few non-missing measurements, then the visit response will be set to NE.

At subsequent visits the above steps will be repeated to determine the TL and overall visit response. When calculating the previous minimum, lesions with intervention should be treated as missing and scaled up (as per step 2 above).

Scaling (applicable only for irradiated lesions/lesion intervention)

If $>1/3$ of TL measurements are missing (because of intervention) then the TL response will be NE, unless the sum of diameters of non-missing TL would result in PD (ie, if using a value of 0 for missing lesions, the sum of diameters has still increased by 20% or more compared to nadir and the sum of TLs has increased by ≥ 5 mm from nadir).

If $\leq 1/3$ of the TL measurements are missing (because of intervention) then the results will be scaled up (based on the sizes at the nadir visit to give an estimated sum of diameters) and this will be used in calculations; this is equivalent to comparing the visit sum of diameters of the non-missing lesions to the nadir sum of diameters excluding the lesions with missing measurements.

Example of scaling

Lesion 5 is missing at the follow-up visit; the nadir TL sum including lesions 1-5 was 74mm.

The sum of lesions 1 to 4 at the follow-up visit is 68 mm. The sum of the corresponding lesions at the nadir visit is 62mm.

Scale up as follows to give an estimated TL sum of 81mm:

$$\frac{74}{62} \times 68 = 81\text{mm}$$

CR will not be allowed as a TL response for visits where there is missing data. Only PR, SD or PD (or NE) could be assigned as the TL visit response in these cases. However, for visits with $\leq 1/3$ lesion assessments not recorded, the scaled-up sum of TLs diameters will be included when defining the nadir value for the assessment of progression.

Lesions that split

If a TL splits into two or more parts, then the LDs of the split lesions should be summed and reported as the LD for the lesion that split.

Lesions that merge

If two or more TLs merge, then the LD of the merged lesion should be recorded for one of the TL sizes and the other TL size(s) should be recorded as 0 cm.

Change in method of assessment of TLs

CT, MRI and clinical examination are the only methods of assessment that can be used within a trial, with CT and MRI being the preferred methods and clinical examination only used in special cases. If a change in method of assessment occurs, between CT and MRI this will be considered acceptable and no adjustment within the programming is needed.

If a change in method involves clinical examination (eg, CT changes to clinical examination or vice versa), any affected lesions should be treated as missing.

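### SAP 3.1.1.1, Step 4 after a CR: a visit with one target lesion unmeasured and another back below the PD threshold is set to CR, while the cleaner visit is set to NE

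*SAP*

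**What the plan says.** The rules are in SAP Section 3.1.1.1, under the paragraph on TL visit responses subsequent to CR. Only three responses are open after a CR: "A CR response can only be followed by CR, PD or NE". The steps are mandatory: "the following rules at the subsequent visits must be applied".

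- Step 1 gives CR when every lesion still meets the CR criteria (0 mm, or below 10 mm for a node).
- Step 2 gives NE. Its trigger is "If some lesion measurements are missing but all other lesions meet the CR criteria".
- Step 3 gives PD when at least one lesion fails the CR criteria and the summed diameters reach the PD threshold.
- Step 4 is the default for everything left over: "If, after steps 1 through 3, a response can still not be determined, the response will be set to remain as CR".

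The paragraph on missing TL data in the same section sets the general rule: "For a visit to be evaluable, all TL measurements should be recorded". Its only exceptions are routes to PD: a new lesion, non-target PD, or a recorded sum that meets PD even with the unrecorded lesions counted as gone.

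**The concern.** Step 2 catches a missing lesion only when all the measured lesions are still clear. If one measured lesion has come back by less than the PD threshold, Step 2 no longer applies and Step 3 is not met. Step 4 then awards CR without asking whether every lesion was measured. More visible disease produces a better score, and the visit is one that the general rule calls not evaluable.

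The TL response feeds the overall visit response (SAP Table 6). From there it feeds confirmation of response (SAP 3.2.2.2), duration of response (3.2.2.3), and PFS censoring with its missed-visit rule (3.2.2.1).

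**Working it through.** No figure in the plan depends on this rule, so there is none to reproduce. The check is to apply the steps literally.

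Inputs:
- Steps 1 to 4 and the missing-TL rule come from SAP 3.1.1.1.
- PD in SAP Table 4 is an increase of 20% or more and of 5 mm or more over the smallest sum.
- Missing lesions count as 0 mm in the PD check.
- A TL too small to measure is entered as 5 mm unless a smaller value was reliably measured.

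In visits A to C and F there are three non-nodal TLs with a nadir sum of 0 mm. In D and E there is one node of 8 mm at nadir and one non-nodal TL at 0 mm.

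| Visit after CR | Steps 1 and 2 | Step 3 (sum minus nadir) | As written | With the fix |
|---|---|---|---|---|
| A: 0, 0, missing | Step 2 met | not reached | NE | NE |
| B: 4 mm, 0, missing | neither met | 4 − 0 = 4 mm, below 5 | CR (Step 4) | NE |
| C: 5 mm, 0, missing | neither met | 5 − 0 = 5 mm, PD by Table 4 | PD | PD |
| D: node 8 mm, other missing | Step 2 met | not reached | NE | NE |
| E: node 12 mm, other missing | neither met | 12 − 8 = 4 mm, below 5 | CR (Step 4) | NE |
| F: 3 mm, 0, 0, all measured | neither met | 3 − 0 = 3 mm, below 5 | CR (Step 4) | CR |

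B scores better than A, and E better than D. The fix removes both inversions. PD visits and fully measured visits are unchanged.

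**Size of the window.** With non-nodal TLs at a nadir of 0, the largest whole-millimetre reappearance still scored CR is 4 mm. If the unmeasured lesion is a node that contributed 8 mm to the nadir sum, a non-nodal lesion back at 12 mm also gives 12 − 8 = 4 mm and CR. That last case holds only if the nadir keeps the missing node. If the nadir is restricted to the lesions measured at the visit, it is PD. B and E do not depend on this reading.

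**Effect on ORR.** Under SAP Table 6, a TL CR with non-target CR or none at baseline, and no new lesion recorded, is an overall CR. It can then confirm an earlier response at least 4 weeks before. One patient is 1/150 = 0.67 percentage points, taking the planned 150 as the denominator.

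**Effect on PFS.** Take scheduled days 225, 281, 337 and 393, with a CR on day 225 and a B-type visit on day 281. Assume that an NE visit does not count as the previous assessment.
- No later scan: censored on day 281 if scored CR, on day 225 if NE. The difference is 281 − 225 = 56 days in the favourable direction.
- Day 337 missed, progression on day 393: if scored CR, the gap is 393 − 281 = 112 days, within the 126-day limit, so progression is an event. If NE, the gap is 393 − 225 = 168 days, so the patient is censored on day 225. Here the false CR is unfavourable.

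**The case against.** The best defence is precedence. The general rule already makes a visit with an unmeasured TL not evaluable unless PD, and Step 4 speaks only of responses that cannot otherwise be determined. A programmer could therefore assign NE before reaching Step 4. That reading is available, but the SAP does not state it. The steps are worded as mandatory, and Step 2 deals with missing lesions inside them, which suggests that they were meant to be complete. Two programmers could follow the text and differ.

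Two stronger readings are tempting and not supported:

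- A reader might infer that regrowth from a nadir of exactly 0 always falls to CR, whatever its size, because a percentage change from 0 is undefined. But the relative test asks for a sum at least 20% above nadir, and any positive sum exceeds 1.2 × 0. The 5 mm test then decides, and a regrowth of 5 mm or more is PD by Table 4. Division by zero is a programming note, not a missed PFS event.
- A reader might take "CR will not be allowed as a TL response for visits where there is missing data" as a direct contradiction. It sits under the scaling rules, which are limited to irradiated or otherwise treated lesions. It goes on to list PR and SD, which are not available after a CR. It supports the principle but does not govern this case; the missing-TL rule does.

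**Conclusion.** The point holds for the missing-lesion case. As written, Step 4 gives a CR to visits that the section's own missing-data rule would call not evaluable, and it ranks them above cleaner visits.

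The case is rare. It needs a prior TL CR, a later visit with an unmeasured TL, and another TL back below the PD threshold. ORR changes only if no other CR or PR pair confirms the response; a patient with PR followed by CR at least 4 weeks later is already confirmed, and only the best-response category might shift. The primary marker endpoint does not use this rule.

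Two inferences about size should be resisted. The documents give no CR rate. An assumed 5 to 10% of 150 would be about 8 to 15 patients, but that counts everyone who reaches CR, not those who meet the further conditions. Nor do all errors favour the drug: the PFS examples go in both directions.

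**What to change.** In SAP 3.1.1.1, limit Step 4 to visits at which every TL was measured, and insert before it: *If any TL measurement is missing and PD is not met, the response is NE.*

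As programming clarifications only:
- State that with a nadir sum of 0 any positive sum meets the relative-increase test, so the absolute test decides.
- Reconcile the absolute threshold. SAP Table 4 includes an increase of exactly 5 mm, while the definition of objective progression in SAP 3.2.2.1 requires more than 5 mm. A TL too small to measure is entered as exactly 5 mm. From a nadir of 0, visit C is therefore PD under Table 4 and falls to Step 4 under Section 3.2.2.1.

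The cost is a few sentences and a small program change. At most a few visits should move from CR to NE.

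### After local treatment of a target lesion, the SAP lets Step 1 compare a measured sum with a scaled-up minimum that leaves the treated lesion out, so progression can be assigned when no lesion has grown

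*SAP*

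**What the plan says.** The rules are in SAP 3.1.1.1 (Target lesions).

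- **PD threshold (Table 4).** "At least a 20% increase in the sum of the diameters of TLs, taking as reference the smallest sum on study", and "the sum must also demonstrate an absolute increase of at least 5 mm".
- **Step 1 after an intervention.** "The diameters of the TLs (including the lesions that have had intervention) will be summed and the calculation will be performed in the usual manner". Progression found in this way is final: "If the visit response is PD this will remain as a valid response category".
- **Steps 2 and 3.** If Step 1 shows no progression, the treated lesion is handled as missing. If at most one third of target lesions are affected, the sum of the others is scaled up and used to assign PD, PR or SD.
- **Later visits.** All the steps, Step 1 included, are repeated. For the reference the SAP says: "When calculating the previous minimum, lesions with intervention should be treated as missing and scaled up (as per step 2 above". The scaling subsection adds that "the scaled-up sum of TLs diameters will be included when defining the nadir value for the assessment of progression".
- **Missing target-lesion data.** An earlier paragraph of the same section bases the nadir on one and the same set of lesions and says that it "can only be taken from assessments where all the TLs had a longest diameter (LD) recorded".

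SAP 3.2.2.1 defines objective progression against the previous minimum sum, so that term is the general reference for PD and is not peculiar to Step 2.

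**The concern.** Read literally, Step 1 at a later visit uses two different lesion sets. The visit sum contains the treated lesion at its measured size. The minimum replaces that lesion by a value projected from how the others behaved. If the treated lesion shrank proportionally less than the others, the gap between its real and projected size counts as growth. If it shrank more, the gap hides real regrowth.

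Visit responses are assigned by program (SAP 3.1.1), so the rule feeds directly into:

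- PFS (3.2.2.1);
- confirmation of response, and so ORR (3.2.2.2);
- DoR for responses already confirmed (3.2.2.3);
- the cut-off for best change in tumour size (3.2.2.7).

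The patients concerned stay in these analyses. PFS runs on regardless of other anticancer therapy, radiotherapy does not count as subsequent therapy for ORR, and Protocol Appendix F 4.2.1 asks for treated lesions still to be measured where possible. Two programmers who read the section differently could derive different PFS dates from the same scans.

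**Working it through.** **Inputs.** From SAP 3.1.1.1: PD needs at least +20% (rounded to one decimal) and at least +5 mm; at most five target lesions; scaling only if at most one third are treated. Lesion sizes in steps 3, 5 and 6 are assumed, except where the SAP's own are named.

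**1. The SAP's own example.** The nadir sum is 74 mm over five lesions and 62 mm without lesion 5, so lesion 5 is 12 mm. The other four measure 68 mm at follow-up. Scaled sum = 74/62 × 68 = 81.16, which agrees with the stated 81 mm. Then 81.16/74 = 1.097 and 68/62 = 1.097, so Step 2 compares like with like.

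**2. Who is in scope.** With at most five target lesions, one treated lesion among three, four or five is within one third; 1/2 and 2/5 are not. So exactly one lesion is treated, in a patient with at least three.

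**3. Example with no growth.** Baseline 30+30+30 mm; lesion 1 is irradiated before week 8.

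| Visit | Sizes (mm) | Measured sum | Scaled sum | Step 1, literal | Step 1, like for like |
|---|---|---|---|---|---|
| Week 8 | 30, 15, 15 | 60 | 90/60 × 30 = 45 | 60 v 90, no PD | 60 v 90, no PD |
| Week 16 | 30, 15, 15 | 60 | 45 | 60 v 45: +33.3%, +15 mm, PD | 60 v 60: 0%, no PD |

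The first visit after treatment is safe because the minimum is still the measured pre-treatment sum. The problem starts at the second.

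**4. General condition.** Let U and T be the untreated and treated sums at the pre-treatment nadir, r = T/U, and u and t the fractions of those sums remaining, stable over two visits. Measured sum = uU + tT. Scaled minimum = u(U + T). PD requires

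uU + tT ≥ 1.2u(U + T), that is t/u ≥ 1.2 + 0.2/r, together with (t − u)T ≥ 5 mm.

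If no lesion has grown since that nadir, t is at most 1, so u can be at most 1/(1.2 + 0.2/r).

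| Target lesions | r | Smallest t/u for PD | Largest u without growth |
|---|---|---|---|
| 3 equal | 1/2 | 1.6 | 62.5% |
| 4 equal | 1/3 | 1.8 | 55.6% |
| 5 equal | 1/4 | 2.0 | 50.0% |
| SAP example sizes | 12/62 | 2.23 | 44.8% |

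**5. Spot checks at the second visit after treatment, literal rule.**

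- SAP sizes, untreated 62 → 24, treated 12 throughout: 36 v 28.6 = +25.7%, +7.4 mm, PD.
- SAP sizes, untreated 62 → 31, treated 12: 43 v 37 = +16.2%, no PD.
- Three 30 mm lesions, untreated 60 → 24, treated 30 → 24 → 22: 46 v 36 = +27.8%, +10 mm, PD although the treated lesion is still shrinking.
- Three 30 mm lesions, all shrinking equally: 36 v 36, no PD. Treated lesion resected: 24 v 36, no PD. Treated lesion shrinking more than the others: 63 v 72, no PD.

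**6. The opposite error.** Baseline 30+30+30; week 8: 0, 30, 30 (scaled sum 90/60 × 60 = 90); week 16: 20, 30, 30. Step 1 sets 80 against 90 and Step 2 sets 90 against 90, so there is no PD. Like for like, 80 against 60 is +33.3% and +20 mm, so PD.

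**The case against.** The strongest reply is that the SAP can be read like for like. Step 1 is to be calculated as usual, and the usual reference is the smallest sum on study. The sentence on the previous minimum refers back to Step 2, which may be meant to confine it there. The scaling subsection explains scaling as comparing the same untreated lesions at both visits, and the missing-data paragraph uses one set of lesions. This stands in part: matched sets look like the intended principle. But no sentence limits the scaled minimum to Step 2, the scaling subsection admits it to the nadir for progression generally, and Step 1 is expressly repeated. The readings are not reconciled.

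The second reply is that the trigger is narrow, and that also stands. The SAP expects an intervention to shrink the lesion; if the treated lesion shrinks at least as much as the others, no false PD arises. The others must also have shrunk substantially since the pre-treatment minimum.

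Three stronger inferences are tempting but not supported:

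- **That the week 8 and 16 example shows a false end of response.** A PR followed by PD at the next scan is never confirmed, so the loss falls on ORR; DoR is affected only where a response was already confirmed.
- **That the scaling subsection also admits ordinary missing measurements to the nadir.** Its heading limits it to interventions, so its loose wording is only a point to tidy.
- **That the missing-data paragraph flatly contradicts the intervention rule.** It serves a different situation; the fault is that the SAP does not say which reference Step 1 takes.

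**Conclusion.** The rule as written can assign progression when no lesion has grown, and can also miss progression. It should be corrected before the response program is final. A reader might infer that progression is assigned whenever a target lesion is treated locally. The documents do not support that: it takes one treated lesion among at least three, a second or later visit after treatment, a treated lesion that kept at least 1.6 to 2.0 times the fraction kept by the others (equal lesions; 2.23 for the SAP's example sizes), and at least 5 mm. The ratios assume stable lesions at the two visits.

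The exposed endpoints are secondary and descriptive in a single-arm study. The primary marker endpoint rests on Investigator-defined progression, and SAP 2.1.1 keeps a patient evaluable even without programmed RECIST progression, so it is not directly affected. The documents do not say how many patients had a target-lesion intervention or how unevenly lesions responded. Any false-PD rate would therefore only restate assumptions, and the effect on median PFS cannot be sized.

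**What to change.** In the intervention paragraph of SAP 3.1.1.1, state two references:

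- **Step 1:** the measured sum is compared with the smallest measured sum of the same full set of target lesions.
- **Steps 2 and 3 only:** for progression, the scaled sum is compared with the smallest of the measured pre-intervention sums and the scaled post-intervention sums. This amounts to comparing untreated lesions with the same untreated lesions. The measured pre-intervention sums must be included: the SAP's own example sets a scaled 81 mm against a measured 74 mm, and at the first visit after treatment no scaled minimum exists yet.

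With this change the example gives 60 against 60 in Step 1 and 45 against 45 in Step 2, so no PD. The regrowth case gives 80 against 60 in Step 1, so PD. Optionally, reword the scaling subsection so that it speaks of lesions missing because of intervention.

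The cost is a few lines of SAP text and one extra running minimum in the RECIST program. No new data are needed.
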